#### 6.2.4.1 Photography

The exploratory endpoints based on photography of face include the following:

- **Change from Baseline in lesion counts based on blinded photographic assessment at each visit**

The number of facial lesion counts (inflammatory and noninflammatory) will be counted by a standardized review of photographs at the visits specified in the Schedule of Activities in **Table 2**.

The change from baseline in total lesion counts based on blinded photographic assessment at each visit (Weeks 2, 4, 8, 12 and 20) will be calculated.

- **Change from Baseline in inflammatory lesion counts based on blinded photographic assessment at each visit**

The change from baseline in inflammatory lesion counts based on blinded photographic assessment at each visit (Weeks 2, 4, 8, 12 and 20) will be calculated.

- **Change from Baseline in noninflammatory lesion counts based on blinded photographic assessment at each visit**

The change from baseline in noninflammatory lesion counts based on blinded photographic assessment at each visit (Weeks 2, 4, 8, 12 and 20) will be calculated.

- Change from Baseline in Parametric Acne Severity (PAS) score based on blinded photographic assessment at each visit**  
 The change from baseline in PAS score based on blinded photographic assessment at each visit (Weeks 2, 4, 8, 12 and 20) will be calculated.
- Change from Baseline in erythema score based on blinded photographic assessment at each visit**  
 The change from baseline in erythema score based on blinded photographic assessment at each visit (Weeks 2, 4, 8, 12 and 20) will be calculated.

### 6.3 Pharmacokinetic Variables

Concentration time data will be collected following imsidolimab administration to evaluate the PK profile of imsidolimab. Samples from subjects having received imsidolimab only will be analyzed for PK; no placebo samples will be analyzed. Pharmacokinetic samples will be collected at the time points indicated in **Table 7** below.

**Table 7 Pharmacokinetic Sample Collection and Time Points**

Study Visit	Pharmacokinetic Sample Time Point
Day 1	Pre-dose
Day 1	2 hours $\pm$ 10 minutes post-dose
Day 15	Anytime
Day 29	Pre-dose
Day 57	Pre-dose
Day 85	Anytime
Day 141	Anytime

Non-compartmental analysis (NCA) will not be conducted due to minimal PK sampling. However, other presentations of PK information may be added at the discretion of the PK scientist.

Population PK modelling may be performed by the Sponsor or another designated vendor, and if done, will be described in a separate PK analysis plan and report.

### 6.4 Immunogenicity Variables

- Presence of ADA to imsidolimab**

Anti-drug antibodies samples will be collected at the time points indicated in **Table 8** below:

**Table 8 ADA Sample Collection and Time Points**

Study Visit	ADA Sample Time Point
Day 1	Pre-dose
Day 15	Anytime
Day 29	Pre-dose

---

Day 57	Pre-dose
Day 85	Anytime
Day 141	Anytime

---

Abbreviations: ADA = anti-drug antibody

ADA assessments will be conducted utilizing a tiered approach that includes:

1. A screening assay that identifies potential binding ADA in serum samples.
2. A confirmatory assay that confirms the binding specificity of the drug.
3. A titer assay that measures the titer of confirmed ADA. A sample that has been found negative in the screening or confirmatory assay will not have a titer value.

A subject will be considered to be positive for imidolimab-induced immunogenicity if the subject has one confirmed positive ADA response after dosing. Confirmed positive ADA samples may also be tested for neutralizing ADA.

Antidrug antibody variables include status (positive or negative) and titers as follows:

- Total subjects with negative ADA response at all times
- Total subjects with confirmed positive ADA response at any time
- Pre-existing immune-reactivity, defined as either
  - A positive ADA at baseline with all post-treatment ADA results negative, or
  - A positive ADA at baseline with all post-treatment ADA responses less than 4-fold over baseline titer levels.
- Treatment-emergent: any post-treatment positive ADA when the baseline ADA result is negative
- Treatment-boosted: any post-treatment positive ADA that is greater than or equal to 4-fold over baseline titer level when baseline is ADA positive
- Overall ADA incidence: the proportion (%) of subjects with positive ADA, either treatment-emergent or treatment-boosted, relative to all imidolimab treated subjects
- Titer values

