9.4 STATISTICAL ANALYSES

9.4.1 GENERAL APPROACH

The statistical analysis will be performed using SAS® Version 9.4 or higher. All details regarding the statistical analysis and the preparation of tables, listings, and figures will be described in the Statistical Analysis Plan (SAP).

Efficacy and Safety of Imsidolimab in Subjects with Acne Vulgaris
Protocol ANB019-209

Version 1.0
11 February 2021

The default summary statistics for continuous variables include number of contributing observations, mean, SD, median, minimum, and maximum. For PK parameters, coefficient of variation (CV) and geometric mean will also be presented, as appropriate.

For categorical variables, the number and percentage (percentage of subjects in each category relative to the total number of subjects in the relevant analysis set or relative to the total number of subjects in the relevant analysis set with assessments available [where appropriate]) in each category will be the default summary presentation.

Unless otherwise specified, “Baseline” is defined as the last observed value of the parameter of interest prior to the first intake of study treatment (this includes unscheduled visits). For numerical variables, change from Baseline will be calculated as the difference between the value of interest and the corresponding Baseline value.

Unless otherwise specified, all formal statistical tests will be 2-sided at the 10% significance level. Point estimates of treatment differences will be accompanied with 2-sided 90% confidence intervals (CIs), where applicable.

In the case of normality assumption violations, appropriate nonparametric methods may be used for analysis.

All data will be presented in by-subject listings.

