### 3.5 Sample Size

Approximately 120 subjects will be stratified based on facial IGA score at baseline (3 [moderate] vs. 4 [severe]) and randomized in a 1:1:1 ratio to receive one of the following study treatments:

- Imsidolimab 400 mg on Day 1, 200 mg on Days 29 and 57

- Imsidolimab 200 mg on Day 1, 100 mg on Days 29 and 57
- Placebo on Days 1, 29, and 57

Assuming a total of 10% of subjects will discontinue prior to Week 12, there will be approximately 108 evaluable subjects (36 subjects in each arm) at the end of Week 12.

The study has 80% power to detect a between-group treatment difference of 6.1 lesions in the primary endpoint of mean change from baseline in the facial inflammatory lesion count at Week 12, using a 2-sided, equal-variance two-sample t-test at the  $\alpha = 0.10$  level, with the assumption of a common standard deviation (SD) of 10.4 lesions. The assumption was based on Arazlo (tazarotene) acne Phase 3 Study Trial-301 results. **Table 1** shows more information on power from a set of scenarios of variability and between-group mean differences.

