### 5.2 Safety Analysis Set

The Safety Analysis Set will include all randomized subjects who receive at least 1 dose of imsidolimab or placebo. The Safety Analysis Set will be used for all safety analyses. Subjects will be analyzed as treated. If a subject receives both treatments, they will be analyzed in the imsidolimab group.

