### 5.5 Populations for Primary Analyses

Demographics will be summarized on the ITT Analysis Set; PP, PK, and Safety Analysis Sets will be tabulated only if they are different from ITT Analysis Set for demographics. Extent of exposure, safety, biomarker, and anti-drug antibody (ADA) data will be summarized on the Safety Analysis Set. PK

parameters will be summarized on the PK Analysis Set. Efficacy analyses will be performed on the ITT and (where indicated) PP Analysis Sets.

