### **7.      STATISTICAL ANALYSIS**

#### **7.1      Data Handling Rules and Definitions, Including Handling of Missing Data**

Except where specified all continuous variables will be summarized with descriptive statistics (the number of non-missing values, mean, SD, median, first and third quartiles, minimum, and maximum). Where data have been logarithmically transformed for analysis, the summary statistics on the back-transformed data will include the geometric mean (calculated as  $\exp(m)$ , where  $m$  is the mean of the data on the log scale) and the coefficient of variation (CV; calculated as  $100\sqrt{\exp(s^2)-1}$ , where  $s$  is the SD of the data on the log scale). All categorical variables will be summarized with frequency counts and

percentages. Tabulations will be provided based on all subjects combined, as well as separately by treatment group.

Missing data will be maintained as missing in the analysis datasets, unless specified otherwise. For variables where missing data are imputed, the analysis dataset will contain a new variable with the imputed value and the original variable value will be maintained as missing.

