## 7.7 Immunogenicity Analyses

ADA status and titer values will be listed by subject and time point. ADA incidences (overall, treatment-emergent, and treatment-boosted) will be tabulated as absolute occurrence (n) and proportion (%) of subjects by treatment group and visit. Descriptive statistics including number of subjects, mean, median, SD, minimum, and maximum of the titer values by treatment group and visit, where possible, will be provided. Neutralizing antibodies, if assayed and present, will also be summarized. The relationship between changes in PK profile and treatment-emergent positive responses will be evaluated to identify a potential impact ADA on imsidolimab exposure. Box plots of ADA status relative to trough concentrations will be plotted. Where possible, evaluation of ADA impact on efficacy and safety may be performed and summarized separately.

All immunogenicity results will be listed.

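### Overall ADA incidence is divided by all imsidolimab-treated subjects, including those with no result that could make them positive; an evaluable denominator would be a cheap improvement

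*SAP*

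**What the plan says.** SAP 6.4, in the definitions below Table 8, gives overall ADA incidence as the percentage of subjects with positive ADA, "either treatment-emergent or treatment-boosted, relative to all imidolimab treated subjects". Treatment-emergent means "any post-treatment positive ADA when the baseline ADA result is negative". Treatment-boosted requires a positive baseline and a post-treatment titer at least 4-fold above it. Each class therefore needs both a baseline and a post-treatment result.

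SAP 5.5 sets the analysis set: "Extent of exposure, safety, biomarker, and anti-drug antibody (ADA) data will be summarized on the Safety Analysis Set". SAP 5.2 defines that set as "all randomized subjects who receive at least 1 dose of imsidolimab or placebo", so membership requires no ADA sample.

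SAP 7.7 adds the tabulation: "ADA incidences (overall, treatment-emergent, and treatment-boosted) will be tabulated as absolute occurrence (n) and proportion (%) of subjects by treatment group and visit". It names the overall incidence explicitly and states no denominator for the by-visit rows.

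On absent data, SAP 7.1 says: "Missing data will be maintained as missing in the analysis datasets, unless specified otherwise". There is no ADA-specific rule for a missing baseline or post-dose sample, and no ADA-evaluable set is defined.

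Protocol 9.4.1 offers two default denominators for percentages. One is the whole analysis set. The other, where appropriate, is "relative to the total number of subjects in the relevant analysis set with assessments available".

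**The concern.** The numerator and denominator are drawn from different groups. The denominator needs one dose; the numerator needs a pair of assay results. A treated subject without that pair can only lower the percentage. Setting assay error aside, the shown figure cannot exceed the rate among subjects who were tested, whatever the reason for the missing samples.

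This also departs from the SAP's own practice. The by-visit proportions for facial IGA, PGI-S and PGI-C in SAP 6.2.3 all restrict the denominator to subjects assessed at that visit. SAP 6.4 gives no reason for treating ADA differently.

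What is at stake is how an exploratory result reads. From the percentage alone, a reader cannot tell a subject who tested negative from one who was not tested, and the error runs in the direction that favours the product. No decision rule in the plan depends on the figure.

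**Working it through.** **Inputs from the documents.** About 120 subjects randomized 1:1:1 (SAP 3.5), so about 40 per arm and 2 × 40 = 80 on imsidolimab. The only attrition figure is in SAP 3.5: "Assuming a total of 10% of subjects will discontinue prior to Week 12". ADA samples are scheduled pre-dose on Day 1 and then on Days 15, 29, 57, 85 and 141 (SAP Table 8). Protocol 8.3.3 asks for a sample at the final visit from subjects who discontinue treatment or are withdrawn.

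**Assumptions.** The documents give no expected ADA rate, no missing-sample rate and no attrition figure for Week 20. The ADA rates below are assumed, at 5% to 30%. The 10% discontinuation figure stands in for the unsampled share at Week 12. Other unsampled shares are assumed.

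**Plan's own figure.** 120 × (1 − 0.10) = 108, or 36 per arm, which agrees with SAP 3.5. On imsidolimab that is 2 × 36 = 72 of 80.

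**Formula for a by-visit row, with a visit-specific numerator and the SAP 6.4 denominator.** Let N be the number treated, m the share with no ADA result at the visit, and p the incidence among sampled subjects.

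Positives counted = N(1 − m)p

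Incidence shown = N(1 − m)p / N = p(1 − m)

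**Week 12, m = 10%, p = 10%.** Positives = 72 × 0.10 = 7.2. With all treated as denominator: 7.2/80 = 9.0%. With sampled subjects as denominator: 7.2/72 = 10.0%.

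**Range.**

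| Unsampled share m | p = 5% | p = 10% | p = 20% | p = 30% |
|---|---|---|---|---|
| 2.5% (assumed) | 4.9% | 9.75% | 19.5% | 29.25% |
| 10% (proxy from SAP 3.5) | 4.5% | 9.0% | 18.0% | 27.0% |
| 20% (assumed) | 4.0% | 8.0% | 16.0% | 24.0% |

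The relative understatement equals m. At m = 10% that is 0.5 to 3.0 percentage points over these rates.

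**Any-time incidence.** The same formula applies, but m is now only the share with no post-dose result at all, or with no baseline result. With five post-dose draws starting at Day 15 and a final-visit sample from those who leave, m should be small. The 2.5% row, 2 of 80 subjects, illustrates this: 10% is shown as 9.75%.

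**Cumulative by-visit numerator.** If a subject once positive stays positive in later rows, the shortfall shrinks. Suppose the 8 subjects gone by Week 12 had already tested positive at the same 10% rate. They add 8 × 0.10 = 0.8, and (7.2 + 0.8)/80 = 10.0%, so nothing is lost. The SAP does not say which numerator applies.

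**The case against.** The strongest reply is that SAP 6.4 attaches the all-treated denominator to one subject-level, any-time variable, and that SAP 7.7 leaves the by-visit denominator open. On that view the by-visit rate is unspecified rather than wrong, and the Protocol 9.4.1 default already permits a sensible choice. This stands in part: the by-visit figures above are conditional. But SAP 7.7 names the overall incidence, and SAP 6.4 gives the only denominator for it, so a programmer following the SAP could well carry it over.

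A reader might infer that the plan counts untested subjects as antibody-negative. It does not. Missing values stay missing, negative at all times is a separate variable, and ADA status is listed by subject and time point. The effect arises only because these subjects sit in the denominator.

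The 10% is a discontinuation assumption made to size the lesion-count endpoint, not a missing-sample rate. Stopping treatment is not leaving the study (Protocol 7.1), withdrawn subjects may be replaced (Protocol 7.2), and the early-termination visit includes the end-of-study procedures. All of this stands, which is why the 10% is used only as a proxy.

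The imprecision of the estimate also dwarfs the shift. With about 40 per arm, 10% is 4 subjects, with an exact 95% interval of about 3% to 24%; one percentage point is 0.4 of a subject. That stands too and limits the importance of the point.

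Finally, an evaluable denominator has its own weakness. It treats unsampled subjects as resembling sampled ones and could overstate incidence if early leavers are less often positive. Requiring a baseline result would also drop a subject with a confirmed post-dose positive, whom SAP 6.4 otherwise counts as positive for drug-induced immunogenicity. Both are met by showing the two denominators together and listing such positives.

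**Conclusion.** This is a cheap improvement. The stated denominator for overall ADA incidence includes subjects who cannot be positive by the SAP's own definitions, so the percentage can only be pulled down. For the any-time figure the effect should be small. For by-visit rows it is a relative understatement equal to the unsampled share, about 10% at Week 12 on the proxy used, provided that the SAP 6.4 denominator is carried over and the numerator is visit-specific. With a cumulative numerator it shrinks and may vanish.

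Two stronger readings are tempting and lack support. One is that the bias is worst at late visits because that is when antibodies are most likely to have developed; the documents say nothing about when ADA develops. Growth over visits would follow only from accumulating missing samples, and no attrition figure is given beyond Week 12. The other is that this incidence is the figure carried forward for the product. The documents do not say so, and both list immunogenicity as an exploratory objective.

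**What to change.** - **SAP 6.4:** define overall incidence among imsidolimab-treated subjects with a baseline and at least one post-dose ADA result. List separately any subject with a confirmed post-dose positive but no baseline result.
- **SAP 7.7:** use subjects with an ADA result at the visit as the by-visit denominator. State whether the numerator is visit-specific or cumulative, and draw numerator and denominator from the same subjects.
- **Tables:** print the number evaluable next to the number treated, so that the all-treated percentage can still be recovered.

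The cost is SAP wording and one extra table row; no new samples or procedures are needed, and Protocol 9.4.1 already allows this kind of denominator. The reported rate becomes slightly less favourable, and it rests on unsampled subjects resembling sampled ones, which a table footnote should say.

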## **6.5 Biomarker Variables**

- **Assessment of biomarkers in tape strips**

The analysis of tape strips biomarkers will be performed by an additional third party designated by the Sponsor.

## **6.6 Safety**

Adverse events, serious adverse events (SAEs), AEs leading to discontinuation of study treatment, and AEs leading to withdrawal from study, as well as changes in vital signs, clinical laboratory parameters (hematology, biochemistry, and urinalysis), and 12-lead electrocardiograms (ECGs) will be evaluated to meet the safety objectives of the study.

### **6.6.1 Study Day and Visit Window Definitions**

Adverse events will be closely monitored on each subject throughout their participation in the study.

Safety assessments for other safety variables will occur as detailed in the Schedule of Activities in **Table 2**.

### **6.6.2 Extent of Exposure to Study Medication and Compliance**

The number of doses received by the subject for a study treatment will be calculated.

The number of days of exposure to a study treatment will be defined as (Date of last treatment – Date of first dose of treatment) + 1.

Total dose received will be the total amount (in mg) of study treatment taken during the treatment period.

Dose intensity for a specified period is defined as (total dose received by a subject during that period/total expected dose during the same period) x 100%.

The expected number of doses for imidolimab treatment arms is as follows:

- Imsidolimab 400 mg/200 mg: 400 mg on Day 1, 200 mg on Days 29 and 57.
- Imsidolimab 200 mg/100 mg: 200 mg on Day 1, 100 mg on Days 29 and 57.

### **6.6.3 Adverse Events**

Adverse events experienced by the subjects will be collected throughout the entire study and will be coded using the version of the MedDRA specified in the approved Data Management Plan. Analysis of AEs will be carried out on the Safety Analysis Set.

An AE is considered treatment-emergent if the date of onset is during or after first dose of study treatment, or if the AE present at Baseline that worsens in either intensity or frequency after first dose of study treatment. An AE that begins on the same date as the first dose of study treatment is treatment-emergent if the AE begins on or after the time of first dose or if the time of AE onset is unknown.

The severity of AEs will be evaluated as “Mild”, “Moderate”, and “Severe” using the criteria specified in **Section 8.2.1.3.1** of the study protocol.

Adverse events will be classified as related, possibly related, unlikely to be related, or unrelated to study treatment using the criteria specified in **Section 8.2.1.3.2** of the study protocol. If the relationship to study treatment is missing, then the relationship will be set to “related” in the summaries of AEs.

Adverse events will be categorized as serious or non-serious using the definition specified in **Section 8.2.1** of the study protocol.

#### **Events with Partial Onset Dates**

All treatment-emergent adverse events (TEAEs) will be included in the tabulations regardless of the completeness of the onset dates. Partial dates will be imputed in order to determine if an AE is treatment-emergent using the rules in **Appendix 1**; however, imputed dates will not be provided in the data listings.

**Uncoded Events:** Before the database lock, uncoded events will be assigned the string “UNCODED” as the body system, and the verbatim term will be used as the preferred term, so they can be included in the summary tables. In the final dataset, all the adverse events will have been coded.

#### **6.6.3.1 Deaths**

All deaths (if any) which occur during the study will be listed.

#### **6.6.4      Laboratory Data**

Clinical laboratory tests that will be performed in this study are summarized in [Appendix 10](#) of the study Protocol. Local laboratory samples will be collected in the eCRF when the central laboratory results are not available immediately, and the Investigator needs to take an immediate decision for any safety concerns, however, local laboratory results will be not used in the summary tables. All laboratory data will be listed, but only hematology, biochemistry, and urinalysis will be summarized.

#### **Conversion to the International System of Units**

All laboratory data will be stored in the database with the units in which they are originally reported. Laboratory data in summary tables and subject data listings will be presented in the International System of Units (SI units). Laboratory data not reported in SI units will be converted to SI units before further processing or data analysis.

#### **Abnormal Values**

Based upon laboratory normal ranges, laboratory test results will be categorized according to the normal range as low, normal, and high. Subjects with laboratory data outside the normal range will be listed with abnormal values flagged.

